From clinical experience, it was observed that many postpartum women with perineal trauma experience several short and long-term physical, physiological, social and psychological postpartum complications such as severe pain, delayed healing of the wound, infection and dyspareunia which may affect the women resumption of function at postpartum period and their future choice of the mode of childbirth. At the same time, there is a lack of statistical documentation on the magnitude of this problem. As well as, there are considerable gaps with implementation of evidence to support management of perineal trauma at postpartum period.

In this context, serious actions should be taken to accelerate the perineal trauma healing and relieve the perineal pain as possible. Most important of these actions is immediate postpartum perineal ice gel pad application, later performance of pelvic floor exercises (Kegel exercises) and perineal warm compresses. These interventions have a lot of advantages as they are not costing, appropriate to postpartum women in many situations, and

safe. Moreover, these interventions promote, accelerate the healing, decrease the perineal pain and facilitate restoration of muscle tone (Farrag, Eswi, & Badran, 2016).

In Egypt, there is a scarce of RCT studies that was conducted in this respect and they have contradicting results. Moreover, almost all these studies were conducted to test only one intervention or compare between two interventions for treatment of perineal trauma but no study tested the impact of a designed protocol of care which starts from immediate postpartum and continues throughout the first week where a combination of therapies is implemented. So, the results of this study will add to the quality of evidence on the effectiveness of postpartum interventions for improving the recovery of postpartum perineal trauma. This protocol may be used as guidelines to be implemented for better quality of patient care.

Aim of the study

The aim of the current study is to test the effect of designed protocol of care on the outcomes of postpartum perineal trauma.

Outcome measures

- **Primary outcomes:** Severity of perineal pain, delayed perineal trauma healing.
- **Secondary outcomes:** Occurrence of infection, postpartum difficulty with turning/rolling in bed, getting out of bed, sitting, walking, defecation and urination.

Research Hypotheses

To fulfill the aim of this study the following research hypothesis is formulated:

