Operational definition of terms

1- A designed protocol of care for postpartum perineal trauma: It is a protocol developed by the investigator based on systematic reviewed studies and randomized controlled trials. The protocol entails a combination of 3 evidence-based therapies for postpartum perineal trauma; application of perineal ice gel pad, pelvic floor exercises (Kegel exercises) and perineal warm compresses applied in steps starting from immediate postpartum and continues throughout the first week in order to relief immediate and sustained perineal trauma.

2- Perineal trauma: Is any injury to the perineum during childbirth which occurs spontaneously (1st or second degree tear) or intentionally through a surgical incision (episiotomy).

3- Postpartum perineal trauma outcomes: It include the following outcomes:

- a- Postpartum perineal pain: It will be assessed by Visual Analogue Scale for pain intensity (VAS).
- b- Postpartum perineal trauma healing: It will be assessed by standardized REEDA scale.
- c- Postpartum perineal trauma infection: It will be assessed by standardized REEDA scale.
- d- Postpartum difficulty with performing functional activities: It refers to postpartum difficulty with turning/ rolling in bed, getting out of bed, sitting, walking, defecation and urination. It will be assessed by Visual Analogue Scale (VAS) for rating functional activities.

Subjects and Methods

Research Design

A randomized controlled trial will be used to fulfill the aim of proposed study. The randomized control trial (RCT) is a trial in which subjects are randomly assigned to one of two groups: one (the experimental group) receiving the intervention that is being tested, and the other (the comparison group or control) receiving an alternative treatment (Spieth et al, 2016).

Sample

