Tool (B) Visual Analogue Scale for Pain Intensity (VAS): It is a standardized linear scale developed by Freyd et al., (1923). It is a self-reported 10 cm horizontal line which represents the subjective estimation of pain intensity. It comprises 0-10-point numerical scale, the two opposite ends representing no pain to severe pain as follows: no pain (0), mild pain (< 4), moderate pain (4 - <8), and sever pain (8-10). This tool is valid and reliable, test-retest reliability coefficient of the VAS has been demonstrated in several studies as $r =0.62$ (Derya, Ergul, Senol, &Aslan, 2017).

Tool (C) Visual Analogue Scale (VAS) for rating functional activities: This tool is adopted from Karakaya et al.,(2012), the difficulty with performing functional activities as (turning/ rolling in bed, getting out of bed, walking, sitting, defecation and urination) will be evaluated by using horizontal 10 cm visual analogue scale for each functional activity, the scale will be applied six times to measure the difficulty with each activity (VAS will be

marked by the women). The scoring for each activity will be as follows: no difficulty (0), mild difficulty (< 4), moderate difficulty (4 - <8), and sever difficulty (8-10). The total score will be recorded (0-60 point), the lowest score (0) indicate no difficulties and the maximum score (60) indicate maximum difficulty. The total score will be interpreted as the following no difficulties (0), Mild difficulties (1 - < 24), Moderate difficulties (24 - < 48), Sever difficulties (48-60). This tool is valid and reliable, test-retest reliability coefficient has been demonstrated as $r = 0.82$ (Karakaya et al., 2012).

Tool (D) Standardized REEDA Scale: This tool is adopted from Davidson (1974), REEDA scale will be used to assess condition of perineal trauma. REEDA scale is a descriptive scale having a four point categorical score (0-3) that measures five components associated with the healing process of perineal trauma. This includes: Redness, Edema, Ecchymosis, Discharge and Approximation of sutures. The total score ranged from 0 to 15 and categorized as the following; 0 to 2 cm good wound healing with no infection, 3 to 5 cm moderate wound healing, 6 to 8 cm mild wound healing, and 9 to 15 cm poor wound healing with infection . This tool is valid and reliable, test-retest reliability coefficient of the REEDA scale has been demonstrated as $r = 0.70$ (Farrag, Eswi, & Badran, 2016).

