Data were statistically described in terms of mean \pm standard deviation (\pm SD), or frequencies (number of cases) and percentages when appropriate. Because the groups are large enough, comparison of numerical variables between the study groups was done using a student t test for independent samples (including statistical analysis of the primary outcomes as perineal pain scores and perineal trauma healing scores among the study and control groups). For comparing categorical data, the chi-square test was performed (including statistical analysis of the difficulties with functional activities; secondary outcome). An exact test was used when the expected frequency was less than 5. Two sided p values less than 0.05 were considered statistically significant. All statistical calculations were done using the computer programme IBM SPSS (Statistical Package for the Social Sciences; IBM Corp., Armonk, NY, USA), release 22 for Microsoft Windows.

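### Functional difficulty is tested by chi-square on severity bands although Tool C yields a 0-60 score, and the plan does not fix the variable, the contact or any multiplicity control

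*Combined protocol and SAP*

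**What the plan says.** - Outcome measures lists, among the secondary outcomes, "postpartum difficulty with turning/rolling in bed, getting out of bed, sitting, walking, defecation and urination". It does not say whether this is one outcome or six.
- Operational definition of terms, item 3(d), treats it as a single item: "Postpartum difficulty with performing functional activities: It refers to postpartum difficulty with turning/ rolling in bed" and the other five activities.
- Tool (C) asks for one line per activity ("the scale will be applied six times to measure the difficulty with each activity") and bands each: "The scoring for each activity will be as follows: no difficulty (0), mild difficulty (< 4), moderate difficulty (4 - <8), and sever difficulty (8-10"). It then adds them ("The total score will be recorded (0-60 point")) and bands the sum: "The total score will be interpreted as the following no difficulties (0), Mild difficulties (1 - < 24), Moderate difficulties (24 - < 48), Sever difficulties (48-60").
- Follow up and monitoring collects the tool in both arms at 24 hours, day 3 and day 5. The day 7 visit lists only REEDA and the pain VAS.
- The Statistical plan uses the independent-samples t test for numerical variables, including both primary outcomes. It uses chi-square for categorical data, "including statistical analysis of the difficulties with functional activities; secondary outcome", with an exact test when expected frequencies fall below 5. The threshold is two-sided 0.05, and no adjustment for multiple tests is stated.

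**The concern.** The 0-60 total is a numerical variable, and the plan already has a test for such variables. Sending functional difficulty to chi-square instead collapses a 60-point scale into four bands. The test then also ignores that the bands are ordered. A real benefit that moves women within a band, or moves few across 24 or 48, can be missed.

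The plan also leaves the analyst free to choose. One test per contact (total) or six (activities) both fit the text, at any of three contacts. If the choice is made after the data are seen, a functional claim at p<0.05 has no known error rate.

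**Working it through.** **1. The plan's own figures.** 6 x 10 = 60, 6 x 4 = 24, 6 x 8 = 48. The range and cuts of the total are the item range and cuts multiplied by six, so the total bands grade a woman's mean over the activities. Severe on the total needs a mean of at least 48/6 = 8.

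**2. What the labels do.** Two activities at 10 and four at 0 total 20: mild overall, with two activities severe. The sum is behaving as a sum; the labels describe different quantities.

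**3. Number of tests.** Total: 1 per contact, 3 over three contacts. Activities: 6 per contact, 18 in all. If the tests were independent, the chance of at least one false positive per contact with six is 1 - 0.95^6 = 26.5%. Positive correlation lowers this.

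**4. Power of the score, by hand (assumed inputs).** The arm size of 50 is from the Sample section. Item SD 2.2 and correlation 0.5 are assumptions.
- SD of total = 2.2 x sqrt(6 + 30 x 0.5) = 2.2 x 4.583 = 10.08.
- Benefit of 0.5 SD on all six: shift = 6 x 1.1 = 6.6; d = 6.6/10.08 = 0.655; noncentrality = 0.655 x sqrt(50/2) = 3.27. With critical value 1.984, power is about Phi(1.29) = 90%.
- Benefit of 0.8 SD on two activities only: shift = 2 x 1.76 = 3.52; d = 0.349; noncentrality = 1.75; power about Phi(-0.24) = 41%.

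**5. Power on the bands, by simulation.** Six equally correlated normal items were limited to 0-10, with means 4, 5, 6.5, 5, 6, 4 (24 h-like) or 2, 2.5, 4.5, 3, 4.5, 2 (day 5-like). Each row uses 3,000 trials of 50 versus 50 at one contact. Chi-square was uncorrected, and totals below 1 were placed in the mild band. The two figures in each cell are 24 h-like / day 5-like, as % of trials with p<0.05.

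| True effect (correlation 0.5) | Chi-square, total bands | t test, total score | Any of six activity chi-squares, unadjusted | Same six, Holm |
|---|---|---|---|---|
| None | 4 / 4 | 5 / 5 | 21 / 20 | 3 / 3 |
| 0.5 SD on all six | 66 / 56 | 91 / 90 | 84 / 86 | 52 / 54 |
| 0.8 SD on all six | 97 / 89 | >99 / >99 | 99 / >99 | 95 / 96 |
| 0.8 SD on two only | 20 / 21 | 42 / 45 | 96 / 95 | 79 / 77 |

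The t-test column agrees with the hand calculation. Monte Carlo error is at most about 1 point (one standard error).

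**6. Range over the assumed correlation (0.3 to 0.7).** With 0.5 SD on all six, total bands give 42-81% and the total score 80-97%. With 0.8 SD on two activities, they give 15-29% and 33-58%. The score had the higher power at every setting tried.

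**7. The gap in the total bands.** A total above 0 and below 1 has no label. Under these inputs with no treatment effect, fewer than 1% of women fall there.

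**The case against.** A reader might infer that the protocol defines the outcome in two conflicting ways. The documents do not support that. Item and total scoring stand side by side in one tool, item 3(d) names one outcome, and the cuts are proportional. Both labels can be reported for the same woman without contradiction.

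A reader might also infer that the two scorings would give the trial different answers. In the simulation they disagree in about 75% of trials when benefit is confined to two activities. No section predicts that pattern, and when all six improve by 0.8 SD the disagreement is only 3-11%. The 20% false-positive figure likewise assumes that any one significant activity would be claimed as a functional benefit, a rule that the plan does not state. The three contacts multiply the tests under either scoring.

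The gap below 1 is trivial, and it disappears if totals are recorded in whole points.

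These objections stand. They do not answer the narrower point: the named test is inefficient for a score that is already being collected, and the plan does not fix which variable, contact or error control applies.

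**Conclusion.** The point holds as a weakness of analysis choice and pre-specification on a secondary outcome. With 50 per arm, item SD 2.2, correlation 0.5 and a moderate benefit across all six activities, banding the total costs roughly 25 to 35 percentage points of power (about 55-65% against about 90%). The loss is smaller when the effect is large. Where benefit is confined to two activities, both analyses of the total are weak (about 20% against 42-45%). Unadjusted testing of the six activities gives about 20% false positives per contact, against a nominal 5%.

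All these sizes rest on assumed means, SD and correlations, because the documents give none. The direction did not change over the range tried. The simulation used plain chi-square throughout, whereas the plan switches to an exact test in sparse tables, so the banded figures are approximate. Perineal pain and healing, the two primary outcomes, are not touched.

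**What to change.** In the Statistical plan, take functional difficulty out of the chi-square sentence. State that the 0-60 total is compared between arms as a score, by the t test already planned for other numerical outcomes, at one of the three contacts. The investigators should name that contact before analysis and make this the single functional test. Report the other contacts, the six activities and any severity bands descriptively. If the activities are to be tested, apply Holm across the six. If the total bands are kept for description, write the mild band as above 0 to below 24. Make Outcome measures and Tool (C) say the same.

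The cost is wording only, with no new data and no more women. The real downside is that a benefit limited to one or two activities is less likely to show on the total, and would have to survive Holm to be claimed. In the two-activity scenario above, at least one activity did so in 77-79% of trials.

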Perineal trauma may lead to short and long-term physical, physiological, social and psychological complications. In the immediate postpartum period the complications include pain, swelling, redness in the area of the surgical wound, dehiscence, hematoma, trauma of the urethra and the anal sphincter. Long-term complications include chronic infections, dyspareunia, anorectal dysfunction, faecal incontinence, urinary incontinence or retention.

Also, 23% – 43% of women continue to experience pain and discomfort in 10 – 12

postpartum days and 7% – 10% of women have long-term pain 3 – 18 months after birth, 23% of women experience surface dyspareunia in the 3rd month, 3% - 10% report of faecal incontinence, and 24% report of urinary problems (Ibrahim, Elgzar, & Hassan, 2017 & Vasileva, Strashilov, & Yordanov, 2019).

Moreover, social and psychological complications associated with perineal trauma affect the woman's ability to care for her new baby and cope with the daily tasks of motherhood and they have a significant impact on daily activities as walking, defecation, urination, self-care, breastfeeding, interfere with the women's sleep, rest, and appetite. These difficulties can cooperate towards negative, painful delivery experiences and may cause mental disorders as postpartum depression. They also change the mother's attitude towards her neonate and affect her sexual function (Mohamed, & El-Nagger, 2017).

In addition, delayed healing of postpartum perineal sutures is a significant health problem that can cause morbidity such as pathologic complication like hematoma, inflammation or even infection. So, acceleration of perineal wound healing during the puerperium is desirable to avoid postpartum women from the dangers of infection or physiological complaints, particular observations and treatments are needed to ensure that the area heals quickly and easily (Magoga et al, 2019).

Several pharmacological and non-pharmacological treatments have been investigated for healing of perineal trauma after vaginal delivery. Traditionally, oral analgesics (non steroidal anti inflammatory agents), local anesthetics (cold and warm sitz baths, lidocaine gel 2%) are used in postpartum care to alleviate perineal trauma. Currently several non-pharmacological therapies are of great importance for the treatment of perineal trauma since they do not cause systemic side effects, such as drowsiness, irritability and changes in the

composition of breast milk (Webb et al, 2019).

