A total of (100) postpartum women with normal spontaneous vaginal delivery and having postpartum perineal trauma will be recruited for this study and randomly assigned to either study group (50) women or control group (50) women. Inclusion criteria will be according to the following; primiparous or 2nd. multiparaous women with postpartum perineal trauma either episiotomy or perineal tear (first and second degree only), age not exceeding 40 years, , body mass index (BMI)within normal 18.5-24.9 kg/m² or overweight 25-29.9 kg/m², free from any high risk condition affecting perineal trauma healing (e.g., diabetes mellitus or obesity), over 37 week gestation and not having any complications during labor and delivery(e.g., abnormal presentation, obstructed labor or delivered with instrument), not having any immediate postnatal complications such as postpartum hemorrhage.

The sample size was calculated using a G-power version 3.1.1 for power analysis. A Power of .95 ($\beta = 1 - .95 = .05$) at alpha .05 (one-sided) was used as the significance level, and effect size= (80%).

Setting

The study will be conducted at postpartum ward of emergency department for labor and delivery in Obstetrics and Gynecology Hospital at Kasr El Aini University Hospital affiliated to Cairo University. Postpartum ward provides care for postpartum women with normal vaginal delivery and post abortion women. The capacity of the ward is 20 beds which provide care for approximately (3000) normal deliveries annually according to local statistics for the year 2020 (Kasr El Aini University Hospital Statistics, 2020).

Tools for Data collection

Required data will be collected by using 5 tools: A) Structured interview schedule; B) Visual Analogue Scale for pain intensity(VAS); C) Visual Analogue Scale (VAS) for rating functional activities; D) Standardized REEDA scale; and E) Postpartum follow up sheet.

Tool (A) Structured Interview Schedule: This tool will be designed by the investigator and will include two sections:

- The first section: Will include four items to assess participants' demographic data such as (age, BMI, educational level, occupation, residence).
- The second section: Will include four items to assess the participants current obstetric history (e.g., obstetric code), type of perineal trauma after delivery (episiotomy, or tears) and degree of perineal tear (1st or 2nd degree tear).

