The primary official permission will be obtained from the research ethics committee of faculty of nursing, Cairo University to approve the tools and the study. Also, the investigator will explain to the women the purpose and nature of the study and its importance. In addition, informed written consents will be obtained from women who were willing to participate in the study after ensuring that their participation is voluntary and the trial posed no risk or hazards on them. As well, each woman will be assured that she has the right to withdraw of the trial at any time without any effect on her care. Then, confidentiality will be assured through coding of data by the investigator and keeping the data in a secret place.

Validity and reliability

Un standardized tools were submitted to 3 experts in the field of maternity nursing to test content validity, clarity of sentences and an appropriateness of content. Modifications were carried out according to the expert judgment.

Procedure

First, the primary official permission will be obtained from the research ethics committee of faculty of nursing, Cairo University to approve the tools and the study. An official permission will be granted from the hospital administrative personnel in the recommended setting to collect the data. Then, data collection will be carried out through five steps in each group: Recruitment & randomization; interviewing; initial assessment; intervention; follow up and monitoring.

Recruitment and Randomization of sample: Women who will meet the eligibility criteria will be recruited from a written list done by the investigator every day. Those plotted in the odd number will be selected until completion of the sample. Random assignment of the subjects into two groups will be done through an opaque sealed envelope reflecting the type of each group, and then the eligible women will be asked to choose an envelope to

determine their groups.

Interviewing: During interview the aim of study will be explained to the women in both groups (study & control group) to gain their acceptance to participate in the study then data related to socio-demographic status and obstetric history will be collected from both groups

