The investigator will provide a clear and concise information through oral and written instructions about the following; 1) The ice gel pad's purpose, benefits, anticipated effects and how to apply it, 2) Apply the ice gel pad on perineum after birth within 30 minutes to an hour, 3) Instruct the women to apply the ice gel pad for about 20 minutes every two hours during the first 24 hours postpartum only, 4) The perineal pad should be changed regularly every two hours to prevent infection. This session will take 30-40 minutes for each woman. Then, six hours after the ice gel pad application, assessment of experienced perineal pain will be done using Visual Analogue Scale for pain intensity (VAS) and assessment of perineal trauma condition will be done using standardized REEDA scale.

Also, six hours after birth women will receive instructions to practice pelvic floor exercises (Kegel exercises) and will be asked to perform these exercises from 6 hours postpartum and continue at home till one week. Before applying the technique, the investigator will teach the women how to recognize the accurate muscle, whereby she imagines holding passing gases or trying to stop the flow of urine midstream at the same time. The women will be taught to insert a clean finger into the vagina before practicing the exercises and if the women feeling pressure around her finger, she is on the right track, the mother also will be instructed to place a hand on her belly during the exercises to make sure that it is kept relaxed.

The investigator will perform vaginal examination while the woman is doing the pelvic floor exercises (Kegel exercises) to ensure correct use of muscles. The investigator

will instruct the women to continue contracting the muscles for about 5 seconds and then to loosen them for 5 seconds and repeat it for five times each set, perform at least five sets per day (total 25 contractions each day will be performed). The mother will be instructed to perform these five sets of exercises at the rest period between other intervention (application of cold compresses for the first 24 hours and application of warm compresses after 48 hours) with at least two hours rest between each set.

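### Women are assured of no risk, but beyond REEDA wound signs, infection and the pain, function and analgesia ratings, no adverse-event question or safety analysis is planned

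*Combined protocol and SAP*

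**What the plan says.** - **Assurance.** Under Ethical consideration, written consent follows an assurance that taking part is voluntary and that "the trial posed no risk or hazards on them".
- **Safety and intended use.** Significance of the study describes the three interventions as "safe. Moreover, these interventions promote, accelerate the healing, decrease the perineal pain and facilitate restoration of muscle tone", and later says "This protocol may be used as guidelines to be implemented for better quality of patient care". The background says of non-pharmacological therapies that "they do not cause systemic side effects, such as drowsiness, irritability and changes in the" composition of breast milk. It does not mention local effects.
- **What only the study arm receives.** A wrapped frozen gel pad is applied for about 20 minutes every two hours over the first 24 hours. Pelvic floor exercises run from six hours to one week, and at the teaching session "The investigator will perform vaginal examination while the woman is doing the pelvic floor exercises". Warm compresses are applied for 15 minutes three times a day from 48 hours to one week. The control arm has routine care only.
- **What is recorded.** Under Tools for Data collection, "Required data will be collected by using 5 tools": an interview schedule, a pain VAS, a functional-activity VAS, REEDA and a follow-up sheet (Tool E). The items listed for Tool E are compliance and need for additional analgesia. The secondary outcomes are "Occurrence of infection, postpartum difficulty with turning/rolling in bed, getting out of bed, sitting, walking, defecation and urination". The Operational definitions assign infection to REEDA.
- **When.** REEDA is scored in both arms at initial assessment, about six hours and day 7. Pain is rated at those times and at 24 hours, day 3 and day 5. Function is rated at 24 hours, day 3 and day 5, and analgesia is asked about at 24 hours.
- **Analysis.** The Statistical plan names pain and healing (t test) and functional difficulty (chi-square or exact test). It does not name infection or adverse events.

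**The concern.** A statement of no risk, or of safety, can come out of a trial only if the trial looks for harm. Here the study arm alone receives repeated cold on a recent wound, warm compresses at home and an additional vaginal examination. These risks may well be small, but the plan does not set out to find out.

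Take a woman whose skin is irritated by a component on day 2, who seeks care on day 3, stops that component and has recovered by day 7. In the planned data she may show a higher pain or function rating and a lower compliance record. Nothing would say what happened, whether she needed care, or why she stopped.

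The report would then show benefit with no account of intervention-specific harm, and readers could take that silence as evidence of none. This matters more if the bundle is later offered as guidance.

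**Working it through.** **1. Stated figure.** The documents give no safety figure to reproduce. The only design number used below is 50 women per arm (Sample). The stated sample-size inputs, reading the 80% effect size as d = 0.8, with one-sided alpha 0.05 and power 0.95, return 35 per arm by t test (70 in total), not 100. Nothing below depends on that difference.

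**2. Exposure set against wound assessments.** In the study arm the second REEDA comes six hours after the first pad. The pad goes on 0.5 to 1 hour after delivery, so this is 6.5 to 7 hours postpartum. The next REEDA is on day 7.

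| Exposure | Amount from the protocol | Share after the 6-hour REEDA |
|---|---|---|
| Cold pad, from 0.5–1 h to 24 h | 24/2 = about 12 applications; 12 × 20 = about 240 min | 17.5/23.5 to 17/23 of the window = about 74% |
| Exercises, from 6 h to one week | 25 contractions a day | practically all |
| Warm compresses, from 48 h to one week | (168 − 48)/24 = 5 days; 5 × 3 = 15 applications; 15 × 15 = 225 min | all |

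**3. What the infection outcome can register.** REEDA has five items scored 0 to 3, for a total of 0 to 15. Totals of 0–2 are labelled as without infection and totals of 9–15 as with infection. The bands from 3 to 8 carry no infection label.
- Two items at their maximum give 3 + 3 = 6, which falls in the 6–8 band.
- A total of 9 needs at least 9/3 = 3 items.
- Maximal discharge with complete loss of approximation, and no other sign, would therefore not count as infection under the 9–15 label.

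**4. Which harms have a place to be recorded.**
- Recorded with a named item: redness, swelling, bruising, discharge and wound approximation at the three REEDA times; pain; six functional difficulties; analgesia at 24 hours.
- No named item: cold or heat injury, a problem after the vaginal examination, unscheduled visits or treatment, and the reason a component was stopped.

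**5. What asking would buy.** With zero events in n women, the one-sided 95% upper limit is 1 − 0.05^(1/n).
- n = 50: 1 − 0.05^(1/50) = 5.8%. The two-sided version, 1 − 0.025^(1/50), is 7.1%.
- If fewer are followed (the documents give no dropout rate): n = 45 gives 6.4% and n = 40 gives 7.2%.

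The chance of at least one event in 50 women is 1 − (1 − p)^50, with p assumed:

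| True rate p | 1% | 2% | 5% | 10% |
|---|---|---|---|---|
| Chance of seeing one or more | 39% | 64% | 92% | 99% |

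The exact power of a two-sided Fisher test at 0.05 with 50 per arm, also under assumed rates, is:

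| Rates compared | 1% v 5% | 2% v 10% | 5% v 15% | 5% v 25% |
|---|---|---|---|---|
| Power | 2% | 19% | 24% | 75% |

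Asking would therefore be informative as a count with an interval, but a between-arm test would add little.

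**The case against.** The strongest reply is that the plan does collect harm-relevant data. A reader might infer that no tool records harms, that wound opening is missed, or that nothing between six hours and day 7 would show. The documents do not support any of these.
- Infection is a named secondary outcome. REEDA includes suture approximation and is scored three times in both arms.
- Both arms are telephoned at 24 hours, day 3 and day 5 about pain and six functions, so a painful or disabling harm would tend to appear there, though without its cause.
- It would also be wrong to say that no bound is possible. Zero cases of REEDA-defined infection on day 7 among 50 women would give the same 5.8% limit for that outcome.
- The categorical tests in the Statistical plan are worded generally enough to cover infection, even though it is not named.

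The conflict with the no-risk assurance should not be overdrawn either. The pads are wrapped and described as approved. The instruction that "The perineal pad should be changed regularly every two hours to prevent infection" is a precaution, not evidence that the trial adds infection risk. No hazard is stated for the vaginal examination. Safety is asserted in background rationale, not as a hypothesis, and guideline use is only a possibility.

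Finally, the consent form is not in the text reviewed, and Tool E is described but not shown. The wording given to women and the final items on the sheet could be better than the protocol suggests.

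All of this narrows the point without removing it. None of it provides an adverse-event question, a wound assessment during home use, or a reason for stopping.

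**Conclusion.** The point holds in a limited form. As described, the trial can give limited comparative data on wound condition and infection at about six hours and day 7, together with pain and function ratings in between. It cannot support a general statement of safety, and the assurance of no risk has no planned data behind it.

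The gap covers about three quarters of the cold-exposure window and all of the warm-compress period. Even after the fix, 50 treated women with no events would exclude only harm rates above about 6% (one-sided) or 7% (two-sided). This assumes that all 50 are followed and that Tool E contains only the items the protocol lists.

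A reader might go further and infer that the bundle is harmful, or that guideline use is ruled out. Neither follows: the documents contain no evidence of harm, and guideline use would rest mainly on efficacy. The missing harms data weaken that case without closing it. The primary pain and healing comparisons are unaffected.

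**What to change.** 1. Add to Tool E one neutrally worded item, asked in both arms at the existing 24-hour, day 3, day 5 and day 7 contacts: any new perineal problem, wound opening, or unscheduled visit or treatment. Ask it before the compliance questions, so that the study arm is not prompted more than the control arm.
2. Add a separate study-arm item on any component stopped and the reason. It cannot be asked identically of women who have routine care only.
3. Report counts by arm descriptively with exact confidence intervals, without relying on a between-arm test.
4. Name REEDA-defined infection in the Statistical plan, with the score rule and time point that define it, since totals of 3 to 8 carry no infection label.
5. Replace the no-risk assurance with a description of the study procedures and a statement that problems will be recorded.

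The cost is a small ethics amendment and a short question at four contacts already scheduled, with no extra visits or women. The drawbacks are that the answers are self-reports from women who know their allocation, and that power to compare arms is low.

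The Statistical plan is written in the past tense. If follow-up is already complete, the remaining step is to report that adverse events were not systematically collected, give the REEDA-defined infection counts, and make no general safety claim.
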